### ***Objectives***

The primary objective is to compare knee-specific health outcomes in patients undergoing TKA performed with VELYS robot-assisted (raTKA) using functional alignment versus TKA performed manually (mTKA) using conventional instrumentation. The primary outcome measure will be differences between the two intervention groups (using an intention-to-treat approach) with regard to change in Forgotten Joint Score (FJS) preoperatively versus 6 months post-surgery. The secondary objectives are to:

- 1) Compare PROMs (FJS, EQ-5D-5L, Oxford Knee Score [OKS], satisfaction [numeric rating scale; NRS], 4-part Likert scale], pain [101-point scale VAS]) at 6 weeks, 6 months, and 12 months;
- 2) Correlate these outcomes with radiographic alignment and intra-operative data;
- 3) Evaluate biomechanical outcomes using motion analysis laboratory assessment;
- 4) Functional and activity-related outcomes;
- 5) Evaluate the economic and efficiency effects of imageless raTKA relative to mTKA;
- 6) Evaluate the human factor effects of introducing a new RAS into healthcare teams;
- 7) Assess surgical safety and the incidence of adverse events in both groups.

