### ***Outcomes***

The primary outcome will be the change in Forgotten Joint Score (FJS) at two timepoints, preoperatively versus 6 months post-surgery. Secondary outcome measures will include PROMs; clinical outcomes; functional, physiological, and technology-enabled activity measures; health service and economic outcomes; technical surgical/radiographic measures, and biomechanical outcomes using motion analysis laboratory assessment. A dedicated motion analysis laboratory (MAL) study will be conducted as a nested sub-study. (Figure 2)

Outcomes	
Primary measure	Change in FJS [pre-surgery, 6 months] 
Secondary Measures	Change in FJS [pre-surgery, 6 weeks, 12 months] Absolute FJS [6 weeks, 6 months, 12 months] OKS [pre-operative, 6 weeks, 6 months, 12 months]  EQ-5D-5L [pre-operative, 6 weeks, 6 months, and 12 months]  Satisfaction Score (NRS, Likert scale) [6 weeks, 6 months, 12 months]  Pain score (VAS) [6 weeks, 6 months, 12 months]  PROM anchor questions  Functional, physiological and technology-enabled activity measures Change in radiographic parameters Alignment measures (HKA, JLO, CPAK, component size and position)  Surgical time (preparation, case, tourniquet & turnaround) NASA TLX & clinician experience (after 1st and every 5th case)  Health service resource utilisation (clinical contacts, analgesic use)

**Fig 2.** Primary and secondary outcome measures. Time points are relative to date of surgery.

FJS: Forgotten Joint Score, OKS: Oxford Knee Score, EQ-5D-5L; EuroQol EQ-5D 5-Level, NRS: numeric rating scale, VAS: visual analogue scale, HKA: hip-knee-ankle axis, JLO: joint line obliquity, CPAK: coronal plane alignment of the knee, NASA TLX: NASA Task Load Index.

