### ***Statistical analysis***

All analyses will adhere to CONSORT reporting standards. A detailed statistical analysis plan will be finalised with the Trial Steering Committee before any formal analyses are undertaken. Baseline characteristics will be summarised to assess comparability between treatment groups. Simple descriptive statistics will follow standard conventions, including means and standard deviations or medians and interquartile ranges as appropriate for continuous variables, and counts and percentages for categorical data.

The primary analysis will examine differences between the two intervention groups (using an intention-to-treat approach) with regard to their change in FJS (preoperatively versus 6 months post-surgery). A Student's independent t-test will be used to compare mean scores between groups. Assumptions of normality and equality of variances will be assessed using diagnostic plots and Levene's test. If variances are unequal, the Welch's t-test will be applied. The results will be reported as mean differences with 95% confidence intervals and p-values.

Secondary outcomes will be analysed similarly, appropriate to the type and distribution of the data. Categorical outcomes, such as patient satisfaction and complication rates, will be compared between groups using the chi-square test. If any expected cell count is less than five, Fisher's exact test will be applied. Effect sizes will be reported alongside these comparisons using risk ratios or odds ratios with 95% confidence intervals to provide a measure of the magnitude and precision of differences between groups.

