### ***Surgical efficiency and task load evaluation***

An assessment of the surgical efficiency, learning curve, physical and cognitive task load costs associated with VRAS raTKA versus mTKA will be conducted. This will include an evaluation of intraoperative timings, NASA Task Load Index (TLX) scores reported by clinicians based on their perception of surgical cases (after the first and every fifth case, including non-trial training period; i.e. after 1st case, 5th, 10th, 15th etc.), and clinician-reported questionnaires.

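### The four-level satisfaction scale is assigned to a chi-square or Fisher test, which is valid but ignores category order, loses power and does not match the promised risk or odds ratio

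*Protocol*

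**What the plan says.** The Statistical analysis section of the Protocol gives a general rule for secondary outcomes: "Secondary outcomes will be analysed similarly, appropriate to the type and distribution of the data". It then applies that rule to categorical data: "Categorical outcomes, such as patient satisfaction and complication rates, will be compared between groups using the chi-square test". The fallback for sparse tables is "If any expected cell count is less than five, Fisher's exact test will be applied". Effect sizes are to be reported "using risk ratios or odds ratios with 95% confidence intervals to provide a measure of the magnitude".

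The Objectives list satisfaction on a numeric rating scale and on a "4-part Likert scale". The outcome table in the Outcomes section repeats both forms at three visits: "Satisfaction Score (NRS, Likert scale) [6 weeks, 6 months, 12 months". No ordinal method is named for the Likert form, and no cut-point for reducing it to two categories.

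The Multiple testing section makes all secondary analyses exploratory. They are reported with unadjusted p-values, effect sizes and 95% confidence intervals.

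**The concern.** A Likert scale runs from worse to better. A Pearson chi-square test on a 2×4 table treats the four levels as interchangeable labels and spreads its sensitivity over 3 degrees of freedom. A general shift towards greater satisfaction, which is the effect of interest, is a one-degree-of-freedom question. The Fisher fallback ignores order in the same way. Neither test says which arm did better.

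The paragraph is also not consistent within itself. If all four levels are kept, the test has no single risk ratio or odds ratio to go with it. If the scale is split in two, the ratio is defined but the cut-point is not, and the result depends on it.

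Dissatisfaction in 10% to 20% of patients is part of the Protocol's rationale in the Introduction, so this outcome will be read closely. A test with avoidably low power makes an inconclusive result more likely and harder to interpret.

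**Working it through.** **Analysable numbers.** The only relevant stated figure is 147 per group (Sample size section: 7 points, SD 24, one-sided 5%, 80% power). By normal approximation, n = 2 × 24² × (1.645 + 0.842)² / 7² = 145.4, so 146; the t-based calculation gives 147. Then 147 / 0.85 = 172.9, so 173 per group and 346 in total. The Protocol's figures reproduce, and n = 147 is used below.

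**Assumptions (not in the Protocol).** Control distribution 50/35/10/5% from most to least satisfied; a consistent shift (common odds ratio, OR) of 1.5 or 1.75; two-sided 5%, in line with the 95% intervals promised.

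**Distribution under the shift.** Divide each cumulative odds of a worse category by the OR. From least to most satisfied, control is 0.050, 0.100, 0.350, 0.500.
- OR 1.5: 0.034, 0.071, 0.295, 0.600
- OR 1.75: 0.029, 0.062, 0.272, 0.636

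**Chi-square, 3 df.** Noncentrality λ = n Σ (p₀ − p₁)² / (p₀ + p₁).
- OR 1.5: λ = 147 × (0.0031 + 0.0048 + 0.0047 + 0.0091) = 3.19; power about 29%
- OR 1.75: λ = 147 × (0.0055 + 0.0087 + 0.0098 + 0.0164) = 5.92; power about 51%

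**Ordinal test, 1 df.** z = ln(OR) × √[n(1 − Σp̄³)/6], with p̄ the mean share over the two arms; power = Φ(z − 1.96).
- OR 1.5: 0.405 × √(147 × 0.799/6) = 1.79; power 43%
- OR 1.75: 0.560 × √(147 × 0.786/6) = 2.46; power 69%

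**Satisfied versus dissatisfied, 2×2.** z = (p₀ − p₁) / √[2p̄(1 − p̄)/n] on the two lowest levels combined.
- OR 1.5: 15.0% against 10.5%; z = 0.0447/0.0389 = 1.15; power 21%
- OR 1.75: 15.0% against 9.2%; z = 0.0584/0.0380 = 1.54; power about 33% to 34%

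**Most satisfied level against the rest, 2×2.** Same formula.
- OR 1.5: 50% against 60%; z = 0.100/0.0580 = 1.72; power 41%
- OR 1.75: 50% against 63.6%; z = 0.136/0.0578 = 2.36; power 66%

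**Simulation.** Simulated 2×4 tables, with a tie-corrected rank test as the ordinal test, agree.

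| Common OR | Chi-square, 4 levels | Rank test |
|---|---|---|
| 1.5 | 28% | 43% |
| 1.75 | 51% | 69% |
| 1.8 | 56% | 73% |
| 2.0 | 71% | 85% |

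The control distribution was also varied to 60/30/7/3% and 40/35/15/10%. Across all three distributions, chi-square against rank-test power was 26–31% against 39–46% at OR 1.5, 49–60% against 67–77% at 1.8, and 64–76% against 80–88% at 2.0. The loss is roughly 12 to 18 points. With no effect, rejection rates were 4.5–4.9% (chi-square) and 4.6–4.9% (rank test), so both hold their level.

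**The case against.** **The chi-square test is not wrong.** It keeps its error rate, and it can detect differences that are not a consistent shift, such as more patients at both extremes. This stands: the complaint is about efficiency, direction and fit with the effect measure, not validity.

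**The Protocol may intend a satisfied/dissatisfied split.** Satisfaction is paired with complication rates and with risk ratios, and the Introduction speaks of a percentage dissatisfied. A 2×2 chi-square would then be routine. That reading is possible, but it does not help: on the assumptions above, that split has the lowest power of the options considered. A split at the top category comes close to the ordinal test, so the result turns on a cut-point that the Protocol does not give.

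**The detail could be left to the statistical analysis plan.** For many secondary outcomes that is fair. Here the Protocol itself names the outcome and the test, so the clause on type and distribution has already been applied. The numeric rating scale is different: the chi-square sentence need not cover it, and no criticism is made of it.

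**A reader might infer a parallel error for NASA Task Load Index scores.** Clinicians rate "after the first and every fifth case, including non-trial training period", and the rule for secondary outcomes follows the sentence "A Student's independent t-test will be used to compare mean scores between groups". One could conclude that repeated, partly non-randomised ratings will be pooled in an independent-groups test. The Protocol does not say so. No test is named for these scores. The quoted words set when ratings are recorded, and the same section gives the learning curve as one purpose, for which training ratings are needed. The t-test is only an inference from a sentence that allows for the type of data. Nor would clustering necessarily exaggerate findings: with arms balanced within clinician and a clinician effect common to both arms, the t-test's standard error is too large and the test is conservative. The model for repeated ratings, and separate reporting of training scores, can be left to the statistical analysis plan.

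**Conclusion.** The point holds for the four-level satisfaction scale only. The Protocol fixes a test that ignores order for an ordered outcome and pairs it with an effect measure that the full table does not supply. The cost is roughly 12 to 18 points of power under a consistent shift. That figure rests on assumed category shares and odds ratios and on 147 analysable participants per group; if the treatment effect is not a consistent shift, the advantage of an ordinal method shrinks or may reverse.

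It would be too strong to call this the wrong test or to expect false-positive findings from it. The consequence is small, because satisfaction is an exploratory secondary outcome and neither the primary comparison nor the sample size depends on it.

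**What to change.** In the Statistical analysis section, take satisfaction out of the chi-square sentence. State that the four-level scale will be analysed by proportional-odds regression, reporting a common odds ratio with its 95% confidence interval and a check of the proportional-odds assumption. A Mann-Whitney test is an acceptable simpler alternative. Keep chi-square or Fisher for binary and unordered outcomes such as complications. If a percentage satisfied is also wanted, name the cut-point in advance and present it as a description.

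The cost is a change of wording and one model check. No added data, visits or participants are needed.

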### ***Multiple testing***

Formal adjustment for multiple comparisons will be applied only to analyses of the primary outcome. Secondary outcome analyses will be considered exploratory and will not undergo multiplicity correction, as such adjustments may be overly conservative and risk masking clinically meaningful effects. Results for secondary outcomes will therefore be presented with unadjusted p-values, effect sizes, and 95% confidence intervals to support interpretation rather than definitive inference.

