### ***Safety and adverse events***

Both raTKA and conventional mTKA techniques are in routine clinical use within the NHS and internationally. Published literature demonstrates that the use of RAS in general, and the VELYS RAS specifically, do not confer an increased risk of adverse events or complications compared with conventional manual techniques. Accordingly, no additional patient risks are anticipated beyond those inherent to standard TKA surgery. These will be monitored and recorded in accordance with standard NHS practice and institutional policies.

AEs will be categorised as 'unrelated' or 'related' to the current study according to predetermined definitions. Related AEs include: surgical site infection; arthroplasty failure; related fracture, or any AE occurring during the surgical admission. AEs will be reported in line with Good Clinical Practice (GCP) and Health Research Authority (HRA) requirements, which will be via the NHS DATIX reporting system, and monitored by the TSC. Device-related issues will be escalated through the institutional Medical Physics & Devices pathway and reported to the manufacturer and the Medicines and Healthcare Products Regulatory Agency (MHRA) where applicable. Auditing of trial conduct may be performed by the Sponsor, in accordance with UK research governance frameworks.

The study has undergone independent R&D governance approval through institutional review by the Medical Physics & Devices Department, Surgeon Group, Information Governance Team, Procurement and Operating Department. These have supported the view that the study poses no material increase in procedural risk and that all equipment and software comply with existing safety and regulatory frameworks.

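### For complications the only between-group effect size named is a ratio, which for events at about 1% or below often cannot show how large an excess is excluded; add a risk difference with a score interval (minor)

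*Protocol*

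**What the plan says.** Safety is the seventh secondary objective in the protocol: "Assess surgical safety and the incidence of adverse events in both groups". The Safety and adverse events section gives examples of what counts as related: "Related AEs include: surgical site infection; arthroplasty failure; related fracture, or any AE occurring during the surgical admission". It gives no expected frequency for any of them.

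The Statistical analysis section fixes how such outcomes are compared. The test is "Categorical outcomes, such as patient satisfaction and complication rates, will be compared between groups using the chi-square test", with a switch for sparse tables: "If any expected cell count is less than five, Fisher's exact test will be applied". The effect measure is a ratio: "Effect sizes will be reported alongside these comparisons using risk ratios or odds ratios with 95% confidence intervals", and its stated purpose is "to provide a measure of the magnitude and precision of differences between groups". The same section also plans "counts and percentages for categorical data" as descriptive summaries.

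The Multiple testing section sets the status of these analyses: "Secondary outcome analyses will be considered exploratory and will not undergo multiplicity correction".

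**The concern.** The protocol names complication rates explicitly and chooses a ratio as the effect measure. A ratio needs events in both arms to be informative on both sides. Specific surgical complications may be rare enough that, in a trial of this size, one arm or both will have none.

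The question a reader brings to the safety data is how large an excess of complications with the robotic technique the trial rules out. If the manual arm is empty, the ratio has no upper limit and the question goes unanswered. If both arms are empty there is no estimate, although 0 of 173 against 0 of 173 is informative on the absolute scale. The effect measure then misses the purpose that the protocol itself gives for it.

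This matters somewhat more because the protocol presents safety as one of the NICE evidence domains it is designed to address, and because it asks readers to interpret secondary outcomes through effect sizes and intervals rather than formal inference.

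**Working it through.** **Inputs.** From the Sample size section: a difference of 7 points, standard deviation 24, one-sided alpha 0.05, power 80%, 147 per group, 15% loss, 173 per group. From Randomisation: 1:1 allocation. Complication rates are not in the document, so true rates of 0.25% to 5%, equal in both arms, are assumed.

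**The plan's own figure.** The normal approximation gives n = 2 × (1.645 + 0.842)² × 24² / 7² = 145.4, so 146. The t-based solution is 146.03, so 147. Then 147 / 0.85 = 172.9, so 173. The stated numbers reproduce, and 173 per arm is used below.

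**Chance of an empty arm.** With q = (1 − p)^173, the chance that a given arm has no events is q, the chance that at least one arm has none is 1 − (1 − q)², and the chance that both have none is q².

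| True rate p | Given arm empty (q) | At least one empty | Both empty |
|---|---|---|---|
| 0.25% | 65% | 88% | 42% |
| 0.5% | 42% | 66% | 18% |
| 1% | 18% | 32% | 3% |
| 2% | 3% | 6% | 0.1% |
| 3% | 0.5% | 1% | about 0 |
| 5% | about 0 | about 0 | about 0 |

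With only 147 per arm, at least one arm is empty in 73% of trials at 0.5% and 40% at 1%.

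**What each measure gives in such tables (173 per arm).** The odds ratio column shows the exact conditional interval; the difference column shows the Miettinen-Nurminen score interval.

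| Events | Odds ratio (95% CI) | Risk difference, points (95% CI) |
|---|---|---|
| 0 v 0 | undefined (0 to infinity) | 0 (−2.2 to +2.2) |
| 1 v 0 | infinite (0.03 to infinity) | 0.6 (−1.6 to 3.2) |
| 3 v 0 | infinite (0.41 to infinity) | 1.7 (−0.5 to 5.0) |
| 5 v 0 | infinite (0.93 to infinity) | 2.9 (0.7 to 6.6) |

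The risk difference has two finite limits in every row.

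**The test.** At 1:1, an expected count is below five when there are 9 or fewer events in total (9 / 346 = 2.6%), and Fisher's test then applies. Enumerating all pairs of binomial outcomes with 173 per arm and equal rates gives this true two-sided size for the planned chi-square/Fisher rule at nominal 5%:

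| True rate | Size of planned rule |
|---|---|
| 0.5% | 0.02% |
| 1% | 0.3% |
| 2% | 1.8% |
| 3% | 3.6% |
| 5% | 4.8% |

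With one arm empty, Fisher's test reaches p < 0.05 only from 6 v 0 (p = 0.030); 5 v 0 gives p = 0.061. For true rates of 3% v 0.5%, the planned rule has 24% power.

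**The case against.** Several points on the other side stand.

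- **The ratio is not the only summary.** A reader might infer that complications will be summarised by ratios alone. The document does not support that: counts and percentages per arm are planned, so the point difference can be read off. What is not planned is a between-arm absolute difference with its interval.
- **The problem is confined to rare events.** At 2% an empty arm is already uncommon, and from about 3% the ratio is usable. A broad category, such as any adverse event during the admission, need not be sparse.
- **A ratio with one empty arm is not worthless.** It keeps one informative limit. With 0 events in the robotic arm and 5 in the manual arm, the exact odds ratio interval is 0 to 1.08, which does exclude a large excess with the robot. The information is lost when the manual arm is empty, or both are.
- **Fisher's test is not an error.** A reader might infer that the safety test is faulty because it runs far below 5%. It is a standard and valid choice, and conservatism with sparse data is a known property. The N−1 chi-square would raise power for 3% v 0.5% from 24% to 43%, but it would still miss that sixfold excess more often than not. Its own size is only 1.0% at 0.5%, and it does not guarantee the 5% level. Replacing Fisher's test is a trade-off, and these analyses are declared exploratory.

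One objection carries less weight: that all of this belongs in the analysis plan. Handling of zero cells and the choice between risk and odds ratio can be left there. But the protocol has already named the effect measure for complications, and an analysis plan that follows it to the letter inherits the gap.

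**Conclusion.** The point holds in a limited form and is minor. The ratio is the only between-group effect size the protocol names for complications. For events with a true rate of about 1% or below, at least one arm will be empty in about a third (at 1%) to nearly nine tenths (at 0.25%) of trials of this size. The ratio then has an interval open at one end, or no value at all, and often cannot show how large an excess is excluded. At 2% this happens in 6% of trials and at 3% in 1%.

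These figures rest on assumed rates, on 173 analysed per arm and on equal true rates. Fisher's test can stay. Because the planned rule's size is only 0.02% to 1.8% for rates of 0.5% to 2%, a non-significant p-value from sparse safety data says very little and should not be taken as evidence of equal safety.

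**What to change.** In the Statistical analysis section, and in the analysis plan, make three changes:

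1. For complications and other binary outcomes, report the risk difference with a Miettinen-Nurminen score 95% confidence interval. It is defined with zero events in one or both arms.
2. Keep the risk ratio with its interval where both arms have events.
3. State that a non-significant p-value for a sparse complication is not evidence of equal safety, and that the interval for the risk difference is the basis for interpretation.

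If Fisher's test is kept, add that its p-value and the score interval can disagree in sparse tables. At 5 v 0, Fisher's p is 0.061 while the interval runs from 0.7 to 6.6 points. In exploratory analyses this is acceptable if it is stated beforehand.

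The cost is wording only; no new data and no change in sample size are needed.

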### ***Multiple testing***

Formal adjustment for multiple comparisons will be applied only to analyses of the primary outcome. Secondary outcome analyses will be considered exploratory and will not undergo multiplicity correction, as such adjustments may be overly conservative and risk masking clinically meaningful effects. Results for secondary outcomes will therefore be presented with unadjusted p-values, effect sizes, and 95% confidence intervals to support interpretation rather than definitive inference.

